During the treatment period, subjects will orally self-administer LC350189 or its placebo for 12 weeks starting on Day 1. To maintain consistency, patients will be instructed to take the investigational product at the same time daily, and to withhold the investigational product until after pre-dose laboratory sampling on the days of scheduled visits (Days 14, 28, 56, and 84). At each visit during the treatment period, blood will be sampled for primary, secondary and exploratory endpoint evaluations, and safety assessments will be performed ([Table 12-1](#)). On Day 1 (Visit 4) PK/PD analysis will be conducted pre-dose and 4 hours post-dose for sparse data. For dense data, additional 2, 8 hours and 12 hours post-dose in subjects, who sign written informed consent for dense PK/PD sampling, will be collected on Day 1. On Day 14 and 28 (Visit 5 and 6), PK/PD analysis will be conducted pre-dose for both sparse and dense data. On Days 56 (Visit 7), blood will be sample at pre-dose and 4 hours post-dose for sparse data; and additional 8 hours post-dose for dense data. On Day 84 (Visit 8), pre-dose blood will be sampled at a single time point for PK trough and PD analyses for both sparse and dense data.

Subjects will record the incidence of gout flares using electronic patient diaries (eDiary) from start of prophylaxis (Visit 2) through to end of treatment (Visit 8).

Subjects enrolled to the study before the implementation of the Protocol version 5.0

[figure not shown]
Upon implementation of the Protocol version 5.0, enrollment to the active control group (febuxostat) will be stopped and subjects will be randomized to one of four groups (LC350189 50 mg, LC350189 100 mg, LC350189 200 mg, or placebo).

Subjects who have already randomized to the active control group (febuxostat) on Day 1 (Visit 4) before stopping enrollment of the active control group will stay in the study and continue receiving the treatment regimen (one capsule from each of 2 bottles of LC350189 placebo and 1 bottle of febuxostat 40 mg or 80 mg) that they are initially assigned to. The subjects will receive febuxostat 40 mg on Day 1 (Visit 4) and continue to be on febuxostat 40 mg for the rest of the treatment period if their sUA is < 6.0 mg/dL on Day 14 (Visit 5). If their sUA is \geq 6.0 mg/dL on Day 14 (Visit 5), they will receive febuxostat 80 mg QD on Day 28 (Visit 6) and will continue to be on this dose for the rest of the treatment period.

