Subjects randomized to the test (LC350189 50 mg, LC350189 100 mg, or LC350189 200 mg) or placebo groups before implementation of the Protocol version 5.0 will stay in the study and continue receiving 3 bottles of investigator products (2 bottles of LC350189 25mg/100mg/placebo and 1 bottle of febuxostat placebo) as they are initially assigned to.

The rest of study procedures will apply as described in Section 6.2 and the SoA ([Table 2-1](#)).

Figure 6-1 Study Design Schematic

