Subjects will be instructed to fast for at least 8 hours (preferably, overnight fast) prior to returning to the clinic on Day 14 (Visit 5), 28 (Visit 6), 56 (Visit 7), and 84 (Visit 8). On Day 14, 28, 56, and 84, subjects will withhold the investigational product until pre-dose laboratory samples have been obtained. Subjects will then take investigational product on site on Day 14 (Visit 5), 28 (Visit 6), and 56 (Visit 7), and blood samples will be obtained at the time points stated in the PK/PD sampling schedule (Section [9.1.14](#), [Table 9-3](#)). The last dose of investigational product that a subject will take is on Day 83. AEs will be recorded and measurements of laboratory parameters, vital signs, and 12-lead electrocardiogram (ECG) will be performed for safety evaluation according to the SOA ([Table 2-1](#)). Subjects will record the incidence of gout flares and rescue treatment using eDiary. Subjects will be assessed for the presence of tophi by palpation at the end of treatment visit (Visit 8). All tophi will be counted and recorded on the Tophi eCRF page.

Visit 9: Follow-up

A Follow-up on site-visit will be performed on Day 98 for safety assessments ([Table 2-1](#)).

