8.4 Dose Regimen

Subjects will receive LC350189 50 mg, LC350189 100 mg, LC350189 200 mg, or placebo. LC350189 or placebo capsules will be packaged in 60 mL bottles, each containing 35 capsules. On Day 1 (Visit 4), the appropriate investigational product per the randomization code will be dispensed. Additional bottles will be dispensed on Day 28 (Visit 6) and Day 56 (Visit 7). At visits where investigational product is being returned and new investigational product is being dispensed, all bottles should be returned for investigational product accountability. In order to facilitate investigational product accountability, the subjects ID as well as the visit number must be filled in on the label before dispensing.

Subjects will self-administer investigational product (two capsules of LC350189/placebo) and one tablet of gout flare prophylaxis orally once daily in the morning, if possible, at approximately the same time each day, with water and without regard to food.

Subjects will self-administer investigational product from the following bottles:

- Subjects randomized to LC350189 50 mg will self-administer one capsule from each of 2 bottles of LC350189 25 mg.
- Subjects randomized to LC350189 100 mg will self-administer one capsule from each of 1 bottle of LC350189 100 mg and 1 bottle of LC350189 placebo.
- Subjects randomized to LC350189 200 mg will self-administer one capsule from each of 2 bottles of LC350189 100mg.
- Subjects randomized to placebo will self-administer one capsule from each of 2 bottles of LC350189 placebo.

Subjects will be instructed to stay adequately hydrated. On Day 1 (Visit 4), investigational product will be taken at site from the bottle handed out at the visit. On Day 14 (Visit 5), investigator product will be taken at site from the bottle dispensed on Day 1 (Visit 4). On Day 28 (Visit 6) and 56 (Visit 7), investigational product will be taken from the bottle newly dispensed and handed out at the visit.

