8.4.1 Compliance

The administration of investigational products will be recorded in the appropriate sections of the eCRF. During the study, subjects will receive a total of 2 bottles for LC350189/ placebo. Subjects who are randomized to the study groups before the implementation of the Protocol version 5.0 will continue receiving a total of 3 bottles for LC350189/febuxostat/placebo. Subjects will be required to bring investigational product containers to each clinic visit, regardless of whether the investigational product container is empty. If a patient is persistently noncompliant with an investigational product, (taking <80% or >120% of the allocated investigational product for the period since the last visit) it may be appropriate to withdraw the subject from the study. All subjects should be re instructed about the dosing requirement during study visits. Compliance will be measured using the following formula:

$$\begin{aligned}(B) \div (C) &= (D) \\ (D) \times 100 &= \% \text{ Compliance}\end{aligned}$$

Where (B) = the total number of capsules minus the number of capsules in the bottle and (C) = the number of days during treatment period.

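### Protocol 8.4.1 compliance formula omits capsules per day: on a pooled count full adherence scores 200% (two bottles) or 300% (three); minor, with a matching slip in one SAP 7.2.2 line

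*Protocol*

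**What the plan says.** Protocol 8.4.1 gives one formula, B ÷ C = D and D × 100 = percent compliance. B is "the total number of capsules minus the number of capsules in the bottle and (C) = the number of days during treatment period". The same paragraph says withdrawal may be appropriate for a persistently noncompliant subject, meaning one "taking <80% or >120% of the allocated investigational product for the period since the last visit".

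The number of capsules per day is set elsewhere:

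- Protocol 8.4, current regimen: "Subjects will self-administer investigational product (two capsules of LC350189/placebo", followed by a list showing one capsule from each of two bottles in every arm. Each bottle holds 35 capsules, and new bottles are supplied on Days 28 and 56.
- Protocol 8.4.1, subjects randomized before version 5.0: they "will continue receiving a total of 3 bottles for LC350189/febuxostat/placebo".
- Protocol 6.1: for the febuxostat arm the regimen is "one capsule from each of 2 bottles of LC350189 placebo and 1 bottle of febuxostat 40 mg or 80 mg". The test and placebo subjects randomized at that stage keep "2 bottles of LC350189 25mg/100mg/placebo and 1 bottle of febuxostat placebo".
- Protocol 6.2: "The last dose of investigational product that a subject will take is on Day 83".

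SAP 7.2.2 uses the same letters with a different rule. It counts only active capsules (in the placebo arm, the LC350189 placebo capsules). It uses (B/2)/C for 50 mg, 200 mg and placebo, where two counted capsules are taken daily, and B/C for 100 mg and febuxostat, where one is. The SAP change history records the move from three capsules to two and a correction to the compliance derivation. However, the subsection on subjects randomized before version 5.0 ends by defining overall compliance as (sum of B)/(sum of C) × 100%, with no division by 2.

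**The concern.** A ratio of capsules to days is a compliance fraction only when one capsule is due per day. Here two or three are due. The definition starts from the total number of capsules, so a site could naturally add up everything dispensed, subtract everything returned and divide by days. That result is inflated by the number of bottles, and it would be read against the 80% and 120% limits in the same paragraph.

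On that count an adherent subject looks heavily over-dosed, and a subject missing about half or more of the doses looks compliant. This is the protocol's only compliance formula, and the protocol, not the SAP, is the sites' instruction. At stake are the site's compliance score and any discretionary withdrawal decision that relies on it.

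**Working it through.** The documents print no compliance result, so there is no figure to reproduce. The check applies the formula to a fully adherent subject attending on the nominal days.

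**Inputs.** Bottles hold 35 capsules and are dispensed on Days 1, 28 and 56 (Protocol 8.4). The Day 28 and Day 56 doses come from the new bottles (8.4). The last dose is on Day 83 (6.2). Dosing days per interval are therefore:

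- Days 1 to 27: 27
- Days 28 to 55: 28
- Days 56 to 83: 28
- Total: 27 + 28 + 28 = 83

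**Formula as written, all capsules pooled.** B = dispensed − left; score = 100 × B/C.

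| Interval | Two bottles | Three bottles |
|---|---|---|
| Visit 4 to 6 | (70 − 16)/27 = 54/27 = 200% | (105 − 24)/27 = 81/27 = 300% |
| Visit 6 to 7 | (70 − 14)/28 = 56/28 = 200% | (105 − 21)/28 = 84/28 = 300% |
| Visit 7 to 8 | 56/28 = 200% | 84/28 = 300% |
| Overall | 166/83 = 200% | 249/83 = 300% |

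Taking C as 84 days changes the overall figures only to 166/84 = 197.6% and 249/84 = 296.4%.

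**Against the limits.** The pooled score equals the number of bottles times average intake across bottles. A score of 80% to 120% therefore means average intake of 80/2 = 40% to 120/2 = 60% on two bottles, and 80/3 = 26.7% to 120/3 = 40% on three.

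**Same formula, one bottle at a time.** Over its own interval: 27/27 = 28/28 = 100%, no error. If C is instead taken literally as the whole treatment period, one bottle gives 27/83 = 33% or 28/83 = 34%. The correct answer thus needs two choices that 8.4.1 does not state: count by bottle, and match C to the bottle's interval.

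**With the divisor restored.** Two bottles: 54/(2 × 27) = 56/(2 × 28) = 100%. Three bottles: 81/(3 × 27) = 84/(3 × 28) = 100%. A fixed divisor of 2 fails for three bottles when all capsules are counted: 81/(2 × 27) = 150%.

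**SAP 7.2.2.** The per-interval rule is correct: (54/2)/27 = (56/2)/28 = 100% for 50 mg, 200 mg and placebo; 27/27 = 28/28 = 100% for 100 mg and febuxostat. The overall line for subjects randomized before version 5.0, with B as the raw count, gives 166/83 = 200% for 50 mg, 200 mg and placebo, and 83/83 = 100% for 100 mg and febuxostat. That contradicts the table above it.

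**The case against.** The strongest reply is that the formula is only loosely worded. It refers to a single bottle, one capsule per day comes from each bottle, and on that reading B/C over the matching interval is exactly 100%. The SAP also uses the term treatment period for a single dispensing interval, so C may be meant that way. This stands, and it is why the 200% and 300% are conditional on pooling. It does not clear the text. Pooling is a fair reading of a definition that begins with the total number of capsules, and the SAP, with the same letters, sums over the counted bottles and then divides by 2 where two are taken daily. Separate counts would also give two or three scores per subject, with no rule for the single percentage that 8.4.1 promises.

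The second reply is that nothing depends on the formula. The withdrawal limit is worded as a share of allocated product, which scales correctly for any number of bottles. It also requires persistence and leaves the decision open. A score of 200% in every adherent subject would probably be noticed at the first accountability visit. SAP 4.4.4 leaves the overall compliance algorithm and the per-protocol cutoff to a blinded data review before database lock. All of this stands and keeps the weight low.

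The third reply is that a pooled share can hide under-use of one bottle. In the 100 mg arm, 60% of the active bottle and 100% of the placebo bottle gives (0.6 + 1)/2 = 80%, inside the limits. In the febuxostat arm, 40% of febuxostat with both placebo bottles fully used gives (0.4 + 1 + 1)/3 = 80%. This is correct, and it is a reason to add a per-bottle score. Counting active capsules only, as the SAP does, is not open to blinded sites.

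**Conclusion.** Minor, but wrong as written. Protocol 8.4.1 lacks a capsules-per-day divisor. On a pooled count, full adherence scores 200% or 300% against limits of 80% and 120%. The figures assume nominal visit days, complete returns and one capsule per bottle per day. The intake bands refer to average intake across bottles.

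A reader might infer that the formula fails on every reading, that adherent subjects were or would be withdrawn, or that the per-protocol set or a comparison between arms is distorted. The documents support none of these. The per-bottle count is correct, nothing shows how sites counted, the withdrawal wording is correctly scaled and discretionary, and the SAP per-interval derivation is right. The number of subjects affected cannot be stated, and no change to an efficacy, safety or disposition result is shown.

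The overall line in SAP 7.2.2 for subjects randomized before version 5.0 is a separate slip of the same kind. It doubles the overall figure for 50 mg, 200 mg and placebo if B is used as the raw count.

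**What to change.** In Protocol 8.4.1, replace the formula with:

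- Compliance = (capsules dispensed − capsules returned, all bottles) ÷ (bottles in use × dosing days since the last dispensing visit) × 100, with 2 bottles under version 5.0 and 3 for subjects randomized earlier, applied at Visits 6, 7 and 8.
- In addition, a score for each bottle: capsules used from that bottle ÷ dosing days × 100, so that under-use of one bottle is not masked.

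In SAP 7.2.2, in the subsection on subjects randomized before version 5.0, change the overall line to (sum of B ÷ counted capsules per day) ÷ (sum of C) × 100%. That is B/2 for 50 mg, 200 mg and placebo, and B for 100 mg and febuxostat.

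The cost is one formula and a sentence or two in the protocol, or a site memo to the same effect, and one line in the SAP. No new data are needed, provided the returned count is kept for each bottle.

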8.5 Gout Flare Prophylaxis

Gout flare prophylaxis will consist of colchicine 0.6 mg (QD) starting at Visit 2 (between Day -30 to -23) through the end of the treatment period.

8.6 Overdose

If a study medication error of greater than 3 pills occurs, it must be documented as a Protocol Deviation. A brief description should be provided in the deviation, including whether the subject was symptomatic (list symptoms) or asymptomatic, and if the event was accidental or intentional.

Dosing details should be captured on the eCRF. If the subject takes a dose of investigational product that exceeds protocol specifications and the subject is symptomatic, then the symptom(s) should be documented as an AE and be reported.

Should an overdose occur, the Investigator or designee should contact the Sponsor or designee within 24 hours.

8.7 Randomization and Blinding

Subjects who meet all of the inclusion criteria and none of the exclusion will be assigned a subject randomization number via an Interactive Web Response System (IWRS) on Day 1 after the wash-out/prophylaxis period that will follow screening (Visit 1), and the study drug blind will be maintained using the IWRS. Blind of the subjects randomized to study groups before the implementation of the Protocol version 5.0 will be maintained by giving treatment regimen (3 bottles of LC350189/febuxostat/placebo) as they are initially assigned to.

Randomization will continue until a total of 152 subjects have been randomized, this total number of randomized subjects will exclude the number of subjects who are assigned to the active control group (febuxostat) before implementation of the active control group elimination. The randomization will be stratified by post-washout/pre-dose sUA (<9.8 mg/dL or \geq 9.8 mg/dL) at Visit 3 and the presence or absence of tophi at screening (Visit 1).

If a subject has experienced a gout flare during the screening and wash-out/prophylaxis period, the subject will not be randomized and can be rescreened once 3 weeks after resolution of gout flare.

If a subject cannot be randomized, the reason will be entered into the screening disposition page.

8.8 Breaking of Blinded Code

The code for a subject may be broken in a medical emergency, if knowing the identity of the treatment allocation would influence the treatment decision of the subject or if demanded by the subject. Whenever a code is broken, the person breaking the code must record the time, date, and reason as well as his/her initials in the source documents. During un-blinding procedure in case of medical emergency, it should be ensured that no study personnel is unblinded to other subjects. Study site personnel and Sponsor personnel directly associated with the conduct of the study will not be unblinded.

If the study site needs to unblind a subject, the Sponsor and Study Medical Monitor must be notified within 24 hours after emergency unblinding.

All codes (whether broken or not) must be kept throughout the study period. Accountability of all broken or unbroken codes (hard copy or electronic) will be performed at or after study closure and codes will be maintained in the Investigator's Site File (ISF) at the site or with the retention product.

8.9 Auxiliary Supply

The Sponsor or delegate will supply laboratory materials necessary for PK/PD sampling, all the safety testing (hematology, biochemistry, and urinalyses [incl. pregnancy test]) in collaboration with the laboratory.

9.0 STUDY PLAN

9.1 Study Procedures

9.1.1 Informed Consent and HIPAA Release

Written informed consent will be obtained from each subject prior to performing any study-specific evaluations. The Health Insurance Portability and Accountability Act (HIPAA) release is included in the informed consent process. The informed consent document is subject to review and approval by the Sponsor and will be approved by a legally authorized representative and a qualified IRB. The IRB-approved document must contain, at minimum, the eight basic elements of informed consent set forth in applicable law. Only the most recently IRB-approved informed consent document must be used to consent prospective study subjects. The Investigator (according to applicable regulatory requirements), or a person designated by the Investigator and under the Investigator's responsibility, will fully inform the potential study subject of all pertinent aspects of the clinical study, including written information given approval/favorable opinion by the IRB/IEC.

Prior to the potential subject's participation in the clinical study, the written ICF must be signed, name filled in, and personally dated by the subject and by the person who conducted the informed consent discussion, and by the Investigator. One copy of the signed and dated informed consent document will be given to the subject and the original retained by the Investigator/site.

9.1.2 Screening

Investigators must account for all subjects who sign ICFs. The Investigator will keep a Subject Screening and Enrollment Log at the investigational site.

If the investigator believes there is an appropriate rationale to perform a retest, which is believed to be due to an intercurrent condition and does not present a safety issue for the subject to participate in the study, a single repeat of test is permitted during the screening period, and all efforts should be made to maintain protocol-defined visit windows.

If a subject has experienced a gout flare during the screening and wash-out/prophylaxis period, the subject will not be randomized and can be rescreened once 3 weeks after resolution of gout flare.

Rescreening of subject who fails screening is allowed one time if the investigator believes there is an appropriate rationale to rescreen the subject and rescreening does not present a safety issue for the subject.

Subjects who meet all of the inclusion criteria and none of the exclusion criteria are eligible for this study and will be invited to participate in the study. Subjects will be instructed on factors influencing study outcomes, such as avoidance of alcohol, prescription or non-prescription medication, and illness/infection. Please refer to Section [7.3](#).

If subjects are fasting (only water for ≥ 8 hours), all screening assessments may be done on the same day. If subjects are not fasting, they will be invited to return for a second screening visit to complete any missing screening procedures (eg. laboratory assessments).

All efforts should be made to maintain protocol-defined visit windows, but if an extenuating circumstance arises preventing this, the Sponsor and/or designee should be consulted. If the Sponsor and/or designee determine that the scientific integrity of data and subject safety would not be compromised, an out of window visit may be permitted.

9.1.3 Demographics and Medical History

Demographic information and medical history, including smoking status and medication history will be obtained at screening.

9.1.4 Physical Examination

The baseline physical examination will consist of the following body systems: (1) eyes; (2) ears, nose, throat, neck, thyroid; (3) cardiovascular system; (4) respiratory system; (5) gastrointestinal system, mouth; (6) dermatologic system; (7) extremities; (8) musculoskeletal system; (9) central and peripheral nervous system and (10) lymph nodes.

9.1.5 Height, Weight, and BMI

Height (without shoes) will be measured once, during screening ([Table 2-1](#)). Weight (without shoes) will be measured with light clothing. BMI (kg/m^2) will be calculated from height and weight.

9.1.6 Vital Signs

Vital signs will include body temperature (aural), blood pressure (after 5 minutes resting), respiration rate and pulse rate (after 5 minutes resting). Vital sign measurements will be performed at days and times indicated in the SOA ([Table 2-1](#)). A single repeat measurement is permitted at screening (Visit 1) for eligibility determination if the investigator believes there is an appropriate rationale to perform a repeat such as due to an intercurrent condition which has quickly resolved.

